3.4. Discussion of Study Design

Dosing will be based on doses that have been shown to be safe in children and adults in multiple studies with normal volunteers and individuals with epilepsy. In this current study, patients will receive OL GNX, prescribed in increments of 15 mg/kg/day up to 63 mg/kg/day given as an oral suspension with food, during a 4-week titration period, 8-week maintenance period, and optional extension period. Patients weighing ≤ 28 kg will be dosed on an mg/kg basis. Patients weighing > 28 kg will be dosed on a fixed regimen in increments of 450 mg/day up to 1800 mg/day.

Ganaxolone will be administered during the 4-week titration period as follows:

1. For patients weighing \leq 28 kg (62 lbs):

- 6 mg/kg three times daily (TID) (18 mg/kg/day) suspension - Days 1-7
- 11 mg/kg TID (33 mg/kg/day) suspension - Days 8-14
- 16 mg/kg TID (48 mg/kg/day) suspension - Days 15-21
- 21 mg/kg TID (63 mg/kg/day) suspension - Days 22-28

2. For patients weighing $>$ 28 kg (62 lbs):

- 150 mg TID (450 mg/day) suspension - Days 1-7
- 300 mg TID (900 mg/day) suspension - Days 8-14
- 450 mg TID (1350 mg/day) suspension - Days 15-21
- 600 mg TID (1800 mg/day) suspension - Days 22-28

Any patient not tolerating the next dose step can be maintained at the lower dose step for additional days before advancing to the next dose. If the next dose is still not tolerated, the patient can drop back to the next lower dose step. A minimum dose of 33 mg/kg/day or 900 mg/day is generally required following the escalation period and during the maintenance period.

Patients will initiate treatment in Part B with GNX at the same dose they were on at the completion of the maintenance period. During the extension period, doses of GNX may be adjusted to a maximum of 600 mg TID for patients weighing $>$ 28 kg and a maximum dose of 21 mg/kg TID for patients \leq 28 kg.

4. STUDY POPULATION

Each patient's parent/LAR must participate in the informed consent process and provide written informed consent (and/or patient assent) before any procedures specified in the protocol are performed.

4.1. Inclusion Criteria (Part A)

The patient will not be considered eligible for the study without meeting all the criteria below.

1. Clinical or mutational diagnosis of TSC consistent with Northrup and Krueger, 2013.
 - a. Molecular confirmation of a pathogenic mutation in *TSC1* or *TSC2*. A pathogenic mutation is defined as a mutation that clearly prevents protein synthesis and/or inactivates the function of the *TSC1* or *TSC2* proteins (e.g., nonsense mutation or frameshift mutations, large genomic deletions) or is a missense mutation whose effect on protein function has been established by functional assessment. The investigator must review the results of the genetic analysis and confirm that the causal relationship to the epilepsy syndrome is likely. OR

b. Clinical diagnosis of definite TSC which includes two major features or one major feature with ≥ 2 minor features. The investigator must document which of the features (Major or Minor) fulfill the clinical diagnostic criteria.

Major features	Minor features

 1. Hypomelanotic macules (≥ 3, at least 5-mm diameter) 2. Angiofibromas (≥ 3) or fibrous cephalic plaque 3. Ungual fibromas (≥ 2) 4. Shagreen patch 5. Multiple retinal hamartomas 6. Cortical dysplasias 7. Subependymal nodules 8. Subependymal giant cell astrocytomas 9. Cardiac rhabdomyoma 10. Lymphangioleiomyomatosis (LAM)^b 11. Angiomyolipomas (≥ 2)^b 	
 1. "Confetti" skin lesions 2. Dental enamel pits (≥ 3) 3. Intraoral fibromas (≥ 2) 4. Retinal achromic patch 5. Multiple renal cysts 6. Nonrenal hamartomas

a. Includes tubers and cerebral white matter radial migration lines
 b. A combination of the two major clinical features (LAM and angiomyolipomas) without other features that does not meet criteria for a definite diagnosis.

2. Male or female patients aged 2 through 65 years, inclusive.
3. Patient/parent/caregiver or LAR willing to give written informed consent/assent, after being properly informed of the nature and risks of the study and prior to engaging in any study-related procedures. Assent for patients over 7 years of age should be obtained, if appropriate.
4. Failure to control seizures despite appropriate trial of 2 or more ASMs at therapeutic doses.
5. Have at least 8 countable/witnessed primary seizures during the 4-week baseline period with at least 1 primary seizure occurring in at least 3 of the 4 weeks of baseline. The primary seizure types are defined as the following: focal motor seizures without impairment of consciousness or awareness, focal seizures with impairment of consciousness or awareness, focal seizures evolving to bilateral, tonic-clonic convulsive seizures, and generalized motor seizures including tonic-clonic, bilateral tonic, bilateral clonic, or atonic/drop seizures. Focal aware non-motor and generalized seizures without motor features, infantile or epileptic spasms, and myoclonic seizures do not count as the primary seizure types.
6. Patient must be approved to participate by the sponsor or its designee (e.g., Epilepsy Consortium) after review of medical history, genetic testing, and patients' seizure types.

7. Patients should be on a stable regimen of ASMs at therapeutic doses for \geq 1 month prior to the screening visit, without a foreseeable change in dosing for the duration of Part A. Vagus nerve stimulator (VNS), ketogenic diet, and modified Atkins diet should be unchanged for 3 months prior to screening and will not count towards the number of ASMs.
8. Patients with surgically implanted VNS will be allowed to enter the study provided that all of the following conditions are met:
 - a. The VNS has been in place for \geq 1 year prior to the screening visit.
 - b. The settings must have remained constant for 3 months prior to the screening visit and remain constant throughout the baseline and Part A.
 - c. The battery is expected to last for the duration of baseline and Part A.
9. Parent/caregiver is able and willing to maintain an accurate and complete daily seizure diary for the duration of the study.
10. Able and willing to take IP (suspension) with food 3 times daily. (GNX must be administered with food).
11. Sexually active female of childbearing potential must be using a medically acceptable method of birth control and have a negative quantitative serum β -human chorionic growth hormone (β -HCG) test collected at the initial screening visit. Childbearing potential is defined as a female who is biologically capable of becoming pregnant. A medically acceptable method of birth control includes intrauterine devices in place for at least 3 months prior to the screening visit, surgical sterilization, or adequate barrier methods (e.g., diaphragm or condom and foam). An oral contraceptive alone is not considered adequate for the purpose of this study. Use of oral contraceptives in combination with another method (e.g., a spermicidal cream) is acceptable. In patients who are not sexually active, abstinence is an acceptable form of birth control.

4.1.1. Inclusion Criterion (Part B)

1. Patients have experienced \geq 35% reduction in primary seizure frequency during the Part A treatment period compared to the 4-week Baseline Period.

4.2. Exclusion Criteria (Part A)

Patients are excluded from the study if any of the following criteria apply:

1. Previous exposure to GNX.
2. Pregnant or breastfeeding.
3. Concurrent use of strong inducers or inhibitors of cytochrome P450 (CYP)3A4/5/7. Any strong inhibitor or inducer of CYP3A4/5/7 must be discontinued at least 28 days before Visit 2, study drug initiation. This does not include approved ASMs.
4. Patients who have been taking felbamate for less than 1 year prior to screening.
5. Patients who test positive for tetrahydrocannabinol (THC) or non-approved CBD via plasma drug screen.

6. Chronic use of oral steroid medications, ketoconazole (except for topical formulations), St. John's Wort, or other IPs is not permitted.
7. Adrenocorticotrophic hormone (ACTH), prednisone, or other systemically administered (non-inhaled) steroids must be discontinued > 28 days prior to screening. Concomitant topical, inhaled or intranasal steroids are allowed and do not warrant exclusion from the study.
8. Changes in any chronic medications within the month (e.g., 30 days) prior to the screening visit. All concomitant medications must have been at a stable in dose for at least 1-month prior to the screening visit unless otherwise noted.
9. Patient is being considered for epilepsy surgery or has undergone surgery for epilepsy within the 6 months prior to screening.
10. Have an active CNS infection, demyelinating disease, degenerative neurological disease, or CNS disease deemed progressive. This includes tumor growth which in the opinion of the investigator could affect primary seizure control.
11. Have any disease or condition (medical or surgical; other than TSC) at the screening visit that might compromise the hematologic, cardiovascular, pulmonary, renal, gastrointestinal, or hepatic systems; or other conditions that might interfere with the absorption, distribution, metabolism, or excretion of the IP, or would place the patient at increased risk. This may include any illness in the past 4 weeks which in the opinion of the investigator may affect seizure frequency.
12. An AST/serum glutamic oxaloacetic transaminase (SGOT) or ALT/serum glutamic pyruvic transaminase (SGPT) $> 3 \times$ the ULN at screening or baseline visits and confirmed by a repeat test.
13. Total bilirubin levels $> 1.5 \times$ ULN at screening or baseline visit and confirmed by a repeat test. In cases of documented, stable medical condition (i.e., Gilbert's Syndrome) resulting in levels of total bilirubin $>$ ULN, the medical monitor can determine if a protocol exception can be made.
14. Patients with significant renal insufficiency, estimated glomerular filtration rate (eGFR) < 30 mL/min (calculated using the Cockcroft-Gault formula or Pediatric GFR calculator or Bedside Schwartz), will be excluded from study entry or will be discontinued if the criterion is met post baseline.
15. Have been exposed to any other investigational drug within 30 days or fewer than 5 half-lives (whichever is shorter) prior to the screening visit.
16. Unwillingness to withhold grapefruit, Seville oranges, star fruit, or grapefruit containing products from diet 7 days prior to the first dose and for the duration of the study.
17. Have had an active suicidal plan/intent or active suicidal thoughts in the past 6 months or have made a suicide attempt in the past 3 years.
18. Known sensitivity or allergy to any component in the IP(s), progesterone or other related steroid compounds.

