Patient rescreening is allowed as agreed by the sponsor and the investigator unless there is a general concern for patient safety or an inability for the patient to become eligible (e.g., GNX allergy, sensitivity or exposure, non-TSC and/or other ineligible epilepsy, chronic prohibited medical condition or treatment). Subsequent screening should take place at least 30 days from the patient's last visit, unless otherwise noted.

Part A includes a 4-week baseline and 4 weeks of IP titration followed by 8 weeks of dose maintenance followed by 2-week taper for those patients not continuing into the Part B OLE period. After meeting all eligibility criteria, approximately 30 patients aged 2 to 65 years (inclusive) with TSC-related epilepsy will be enrolled to receive GNX for a total of 12 weeks (4-week titration, 8-week maintenance) in addition to their standard anti-seizure medication(s) (ASMs). Patients will be titrated to 63 mg/kg/day (maximum 1800 mg/day) over 4 weeks, and then maintained at that dose for another 8 weeks. Patients who are not able to tolerate 63 mg/kg/day (or maximum 1800 mg/day) may be maintained on a lower dose after discussion with the sponsor medical monitor. A minimum dose of 33 mg/kg/day or 900 mg/day is generally required during the maintenance period.

For Part A, dose changes including alternative dosing paradigm (e.g., lower dose during the daytime and higher dose in the evening) should be discussed with the sponsor medical monitor

prior to making the change or within 48 hours of making the change. Patients who discontinue GNX should undergo a 2-week taper period, unless otherwise medically indicated. Patients who discontinue GNX before the completion of the maintenance period will continue to be followed per protocol and, at a minimum, patients will be encouraged to maintain daily seizure diaries until the maintenance period in Part A is completed. These patients will also return to the site 2 weeks after the taper for safety follow-up assessments.

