4.5.1. Patient Withdrawal Criteria

All patients or his/her parent/LAR reserve the right to withdraw from the clinical study at any time, as stated in the informed consent/assent form. The investigator may discontinue patients from the clinical study for any of the following reasons:

- Patient is found to have entered the study in violation of the protocol;
- Patient requires the use of a disallowed concomitant medication;
- Patient's condition changes after entering the clinical investigation so that the patient no longer meets the inclusion criteria or develops any of the exclusion criteria;
- Patient or parent/LAR withdraws consent or assent to participate in the study;
- Patient is noncompliant with the procedures set forth in the protocol;
- Patient experiences an AE/SAE that warrants withdrawal from the study;
- Laboratory, medical, or clinical finding for which clinical intervention should take precedence over study participation; or
- It is the investigator's opinion that it is not in the patient's best interest to continue in the study.

Decisions to discontinue the study will be made at each participating site by the investigator. If feasible, the reason for discontinuation should be discussed with the sponsor's medical monitor prior to patient's discontinuation. Patients who discontinue IP during the maintenance period of Part A will continue to record daily seizure frequency at minimum until the completion of the maintenance period.

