5.2. Concomitant Medications

Concomitant medications refer to all treatment taken between the date of Informed Consent/Assent and the date of the last dose of IP. Concomitant treatment information must be recorded on the appropriate eCRF page. Concomitant topical and intranasal steroids for dermatologic reactions and allergic rhinitis are allowed as needed and do not warrant exclusion from study. If the patient is currently taking an excluded medication at the time of the screening

visit, then the patient must undergo a washout period equivalent to 5 half-lives of the drug before they may enter the prospective 4-week baseline period.

Use of dietary supplements or herbal preparations are permitted if patient has been using them consistently for more than 6 months prior to screening and does not plan on changing the dose for the duration of the maintenance period. Use of St. John's Wort is not permitted (See Section 12.1).

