5.2.1. Concomitant AED Medications

Patients in the study should be on a stable regimen of AED medications at therapeutic doses for \geq 1 month prior to the screening visit, and cannot be changed at any time prior to Visit 5 during Part A, but may be adjusted during Part B.

Vagus nerve stimulator, ketogenic diet, and modified Atkins diet should be unchanged for 3 months prior to screening and will not count towards the number of ASMs.

Patient with surgically implanted VNS will be allowed to enter the study provided that all of the following conditions are met:

- The VNS has been in place for \geq 1 year prior to the screening visit.
- The settings must have remained constant for 3 months prior to the screening visit and remain constant throughout the baseline and Part A.
- The battery is expected to last for the duration of the baseline and Part A.

The use of felbamate is allowed provided that the patient has been maintained on a stable dose of felbamate for at least 1 year, and has had stable liver function (AST/ALT) and hematology during the course of treatment, and is expected to remain constant throughout the 12-week treatment period.

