5.4. Excluded Medications

Excluded medications include all steroid medications, other IPs, as well as ketoconazole, and St. John's wort. Concurrent use of ACTH, prednisone or other glucocorticoid is not permitted, nor use of moderate or strong inducers or inhibitors of CYP3A4/5/7. Patients on ACTH, prednisone, or other systemically (non-inhaled) administered steroids should be off the product greater than 28 days prior to screening. Any strong inhibitor or inducer of CYP3A4/5/7 must be discontinued at least 28 days before Visit 2, study drug initiation. A list of CYP3A4/5/7 inhibitors and inducers is included in Section 12.1. Concomitant topical and intranasal steroids for dermatologic reactions and allergic rhinitis are allowed as needed and do not warrant exclusion from the study.

Products containing THC or non-approved CBD are excluded in the treatment period (Part A) of the study but allowed in the OLE period (Part B). Tetrahydrocannabinol or non-approved CBD should be washed out for at least 6 weeks. Patients with a positive result on THC at the

screening and baseline visit will be excluded. Patients with a positive result on CBD without a prescription for an approved CBD would also be excluded.

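### Protocol 5.4 bars moderate and strong CYP3A4/5/7 agents with no ASM exemption, while exclusion item 3 bars strong agents only and exempts approved ASMs

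*Protocol*

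**What the plan says.** Four parts of the protocol bear on CYP3A-active co-medication.

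- **Exclusion item 3 (Protocol 4.2, and the same item in the synopsis).** Concurrent use of strong CYP3A4/5/7 inducers or inhibitors is an exclusion. A strong agent "must be discontinued at least 28 days before Visit 2, study drug initiation. This does not include approved ASMs".
- **Protocol 5.4, Excluded Medications.** After ruling out ACTH and glucocorticoids, the text continues "nor use of moderate or strong inducers or inhibitors of CYP3A4/5/7". It repeats item 3's 28-day stop rule for strong agents but leaves out the ASM exemption that follows it in item 3. It refers the reader to Appendix 1 (12.1) for a list.
- **Protocol 5.2, Concomitant Medications.** If an excluded medication is in use at screening, "the patient must undergo a washout period equivalent to 5 half-lives of the drug before they may enter the prospective 4-week baseline period".
- **ASM stability.** Inclusion item 7 (4.1) asks for a stable ASM regimen for at least 1 month before screening, "without a foreseeable change in dosing for the duration of Part A". Exclusion item 8 (4.2) rules out "Changes in any chronic medications within the month (e.g., 30 days) prior to the screening visit". Section 5.2.1 says that AEDs "cannot be changed at any time prior to Visit 5 during Part A".

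Appendix 1 has two columns, strong inhibitors and strong inducers. It says that it is not a complete list and sends questions about other drugs to the medical monitor.

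**The concern.** Eligibility is decided from 4.2, and concomitant medication is checked against 5.4 at every visit (Protocol 5). If the two differ in scope, one patient can be eligible under the first and on a disallowed drug under the second. GNX is given on top of each patient's standard ASMs (Protocol 3.1), and the sponsor wrote an ASM exemption into item 3, so patients on a CYP3A-active ASM were foreseen.

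Three things are at stake.

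- **Eligibility and patient care.** About six sites (Protocol 3.3) could resolve the difference in different ways. On the literal reading, an ASM would be withdrawn from a patient with refractory epilepsy in order to enter the study.
- **Discontinuation.** "Patient requires the use of a disallowed concomitant medication" is among the listed reasons for which the investigator may discontinue a patient (4.5.1).
- **The PP population.** SAP 2.2 leaves major violations to be defined before database lock, and the study is open-label. The PP repeat is the only sensitivity analysis planned for the primary endpoint (SAP 4.2.1.2). Whether a patient on an exempt ASM belongs in it depends on which section is read.

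**Working it through.** The plan gives no figure to reproduce, and the sample size was not set by statistical methods (Protocol 9.4). The check is a comparison of the rules.

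**Step 1. Classify agents by potency and ASM status, and apply each rule.**

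| Class of agent | 4.2 item 3 and synopsis | 5.4 | Same treatment? |
|---|---|---|---|
| Strong, not an ASM | Excluded; stop 28 days before Visit 2 | Barred; same stop rule | Yes |
| Moderate, not an ASM | Not an exclusion | Barred | No |
| Strong, approved ASM | Exempt | Barred; no exemption stated | No |
| Moderate, approved ASM | Not an exclusion | Barred; no exemption stated | No |

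Three of the four classes are treated differently.

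**Step 2. Follow 5.2 for the two ASM classes.** Section 5.2 does not cite 5.4 by number, but 5.4 is the section headed Excluded Medications, so the link is the natural reading. An ASM barred by 5.4 and in use at screening must then be washed out before baseline. Stopping it after screening breaks 5.2.1 and inclusion 7. Stopping it shortly before screening breaks inclusion 7 and exclusion item 8. Rescreening at least a month later could satisfy both of those items, but only after an ASM had been withdrawn for the sake of the study. No route follows 5.4 with 5.2 and also leaves the ASM in place as item 3 allows.

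**Step 3. Follow 5.2 for moderate agents that are not ASMs.** The 28-day stop rule in 5.4 covers strong agents only, so the washout for a moderate agent comes only through 5.2. Appendix 1 lists no moderate agents, so each case goes to the medical monitor. A patient who does not take the agent satisfies both 4.2 and 5.4. For this class 5.4 is stricter than 4.2, and the two can be followed together.

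**Step 4. Can an ASM exemption be read into 5.4?** Section 5.4 does state an exception where it wants one: it excludes THC and non-approved CBD, and so leaves prescribed approved CBD outside the bar. Its silence on ASMs is therefore not a safe basis for an implied exemption, although the ASM-specific text elsewhere points that way.

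**Step 5. How many patients?** The documents do not classify any named ASM by CYP3A potency, and no ASM appears in Appendix 1. They give no distribution of co-medication. The number affected cannot be derived.

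**The case against.** The best reply is that 5.4 is a general list and every ASM-specific passage points the other way: item 3 exempts approved ASMs, in two places; inclusion 7 and 5.2.1 fix the background regimen; and the whole design adds GNX to standard ASMs. An investigator who washed out an ASM would breach 5.2.1. This stands as evidence of intent. It does not remove the conflict, because 5.4 does not say that ASMs are exempt and 5.2 is worded as mandatory.

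The second reply is that the moderate, non-ASM case is an additional restriction with a medical-monitor route, not a contradiction. That also stands. It remains a mismatch in scope between the entry criterion and the medication rule, and it should be removed in the same edit.

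The third reply is that the effect on results is remote. The primary summary uses the ITT population and all available Part A seizure data, whether or not the patient stopped IP or took rescue medication (SAP 4.2.1.1). It is descriptive, with no hypothesis test (SAP 2.1). Discontinuation under 4.5.1 is at the investigator's discretion. Major violations will be defined before lock, which gives an occasion to settle the point. All of this stands, and it limits the weight of the finding.

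A reader might infer that background ASMs will in practice be withdrawn, or that the PP population will shrink by some stated amount. The documents do not support either. The first goes against the evident intent. The second needs a count of patients on such agents, and the documents have none.

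**Conclusion.** The inconsistency is real and lies in operative text. Item 3 and the synopsis set one scope and an ASM exemption. Section 5.4 sets a wider scope with no exemption, and 5.2 turns the difference into a washout that, followed as written, gives the wrong result for patients on a CYP3A-active ASM.

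Its size is modest. Three of the four classes of agent are affected on paper, but only the two ASM classes produce a direct clash with other requirements, and the intent there is fairly clear. The number of patients is unknown. The primary ITT summary is not invalidated, because PP membership does not alter it. The exposure is to inconsistent eligibility between sites, discretionary discontinuation of patients whom 4.2 admits, and an undecided rule for PP membership in an open-label study.

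The conclusion rests on one reading: that an excluded medication in 5.2 means one listed in 5.4. If 5.2 were meant more narrowly, the washout clash would fall away, but the difference between 4.2 and 5.4 would remain. The correction should be made, but nothing here calls for a change of design.

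**What to change.** 1. In 5.4, add item 3's sentence exempting approved ASMs.
2. In 5.2, state that exempt ASMs are not excluded medications, so the washout does not apply to them.
3. Use one potency scope in the synopsis, 4.2 item 3 and 5.4. The sponsor should choose between strong agents only, which matches Appendix 1 as it stands, and moderate and strong agents, in which case moderate agents are added to item 3 and to Appendix 1. The documents give no pharmacological ground for preferring either. The ASM exemption stays in both cases.
4. In the PP definition (SAP 2.2), state that use of an exempt ASM is not a major violation.

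The cost is a sentence in 5.4, a clause in 5.2, an aligned phrase in up to three places, a line in the SAP and, under the wider scope, an addition to Appendix 1. No new data or analyses are needed: concomitant medication is already recorded (Protocol 5.2) and coded, with AEDs presented separately (SAP 4.1.5).
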